5.4. Major Secondary Endpoint

The major secondary endpoint is clinical remission at Week 12.

5.4.1. Definition

Clinical remission: the Mayo score ≤ 2 with no individual subscore >1 .

5.4.2. Main Estimand (Estimand 4)

The attributes and strategies for the ICEs that were used for the primary estimand (Estimand 1, defined in Section 5.3.2) will also be used for the main estimand (Estimand 4) for the major secondary endpoint.

5.4.3. Analysis Methods for the Main Estimand (Estimand 4)

5.4.3.1. Main Estimator (Analysis) for the Main Estimand

The major secondary endpoint will be analyzed based on the Main Estimand (Section 5.4.2). After accounting for the ICEs for the main estimand, participants who have a missing clinical remission status at Week 12 will be considered not to be in clinical remission at Week 12 (i.e. nonresponder imputation).

In this analysis for the major secondary endpoint, data from all participants in the FAS will be analyzed according to the randomized study intervention regardless of the study intervention they actually received. The treatment difference between combination therapy versus each monotherapy will be tested using a CMH chi-square test stratified by corticosteroid use at baseline (yes, no). The magnitude of the treatment difference will be estimated by the difference in the proportion of participants achieving clinical remission at Week 12 between combination therapy and each monotherapy with a 2-sided 80% CI calculated based on Wald statistic.

The testing of the major secondary endpoints will occur at a 2-sided significance level of 0.2 regardless of the significance of the primary endpoint. No adjustment for multiple comparisons will be made and nominal p-values will be presented.

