A sample size of 210 participants (70 per intervention group) was determined by the power to detect a significant difference in the proportion of participants in clinical response at Week 12 (primary endpoint) between the combination therapy and both monotherapies using a 1-sided chi-square test with 0.1 significance level for each comparison. The study is sized such that the combination therapy has approximately 80% power based on simulations to achieve both comparisons to monotherapy for the primary endpoint. The proportion of participants in clinical response at Week 12 is assumed to be 75% for the combination therapy, which is based on the additive effect from both monotherapies (20% improvement from each monotherapy relative to a historical placebo response of 35%).

Efficacy Analyses

All randomized participants who receive at least 1 dose of study intervention will be included in the efficacy analyses. Participants will be analyzed according to the treatment group to which they were randomized regardless of the treatment they received.

For testing of the primary endpoint, the efficacy of combination therapy versus each monotherapy will be compared. For both statistical comparisons of the primary endpoint, a Cochran-Mantel-Haenszel (CMH) chi-square test stratified by concomitant use of corticosteroids at baseline (Y/N) will be used. The testing will be done simultaneously at the 1-sided 0.1 level of significance for each comparison. The study will be considered positive if the combination therapy group is significantly different from both monotherapy groups for the primary endpoint.

If both tests of the primary endpoint are positive, a CMH chi-square test (1-sided) stratified by concomitant use of corticosteroids at baseline (Y/N) will be used to compare the efficacy of the combination therapy to each monotherapy for the major secondary endpoint. The testing will be done simultaneously at the 1-sided 0.1 level of significance for each comparison.

Analyses for other efficacy endpoints will be performed with no adjustments made for multiple comparisons and nominal p-values will be provided.

Safety Analyses

Safety data, including but not limited to, AEs, serious adverse events (SAEs), infections, serious infections, and changes in laboratory assessments will be summarized. Treatment-emergent AEs will be summarized by treatment group and Medical Dictionary for Regulatory Activities (MedDRA) system organ class and preferred terms.

Other Analyses

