9. STATISTICAL CONSIDERATIONS

Statistical analysis will be done by the sponsor or under the authority of the sponsor. A general description of the statistical methods to be used to analyze the efficacy and safety data is outlined below. Specific details will be provided in the SAP.

Descriptive statistics (eg, mean, median, standard deviation [SD], interquartile range, minimum, and maximum) will be used to summarize continuous variables. Counts and percentages will be used to summarize categorical variables. Graphical data displays (eg, line plots) may also be used to summarize data.

Analyses suitable for categorical data (eg, chi-square tests, Cochran-Mantel-Haenszel [CMH] chi-square tests, or logistic regression, as appropriate) will be used to compare the proportions of participants achieving selected endpoints (eg, clinical response). In cases of rare events, the Fisher's exact test will be used for treatment comparisons. Continuous response parameters will be compared using an analysis of variance (ANOVA) or analysis of covariance (ANCOVA), unless otherwise specified. If the normality assumption is in question, an ANOVA or ANCOVA on the van der Waerden normal scores will be used.

Unless otherwise specified, the analysis of endpoints related to the endoscopy subscore, including the Mayo score, will be based on the final reported endoscopic subscore as defined in Section 8.1.1.

All statistical testing will be performed at a significance level of 0.1 (1-sided) unless otherwise specified. Nominal p-values will be displayed for all treatment comparisons.

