9.2. Sample Size Determination

A sample size of 210 participants (70 per intervention group) was determined by the power to detect a significant difference in the proportion of participants in clinical response at Week 12 (primary endpoint) between the combination therapy and both monotherapies using a 1-sided chi-square test with 0.1 significance level for each comparison. The study is sized such that the combination therapy has approximately 80% power (based on simulations) to achieve both comparisons to monotherapy for the primary endpoint.

The assumptions for the sample size calculations were based on data from the past golimumab programs conducted by the sponsor in participants with UC who were naïve to biologic therapy. The proportion of participants in clinical response at Week 12 is expected to be 55% for golimumab compared to 51% observed at Week 6 in study C0524T17 (PURSUIT), as the PURSUIT program suggested that the response rate might increase slightly with further treatment. This was also confirmed in study CNTO148UCO2001 (PROgECT).⁶⁰ The tested dose of guselkumab is assumed to have the same clinical response rate as golimumab at Week 12. The proportion of participants in clinical response at Week 12 is assumed to be 75% for the combination therapy, which is based on the additive effect from both monotherapies (20% improvement from each monotherapy relative to a historical placebo response of 35%). The different combinations of clinical response rate assumptions and associated power are displayed in [Table 4](#).

Golimumab (n=70)	Guselkumab (n=70)	Combination Therapy (n=70)	Power
50%	50%	70%	79%
50%	55%	70%	66%
55%	60%	75%	69%
55%	55%	75%	81%
55%	60%	80%	90%
60%	60%	80%	85%

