9.4.1.3. Major Secondary Endpoint Analyses

The major secondary endpoint is clinical remission at Week 12 defined as Mayo score ≤ 2 with no individual subscore > 1 . Note: Other remission definitions may be considered and will be fully described in the SAP.

Participants who meet 1 or more treatment failure rules (as specified for the primary endpoint) before Week 12 will be considered not to be in clinical remission at Week 12.

Participants with a missing Mayo score (ie, all 4 Mayo subscores are missing) or who do not return for evaluation at Week 12 will be considered not to be in clinical remission at Week 12.

If both tests of the primary endpoint are positive, a CMH chi-square test (1-sided) stratified by concomitant use of corticosteroids at baseline (Y/N) will be used to compare the efficacy of the combination therapy to each monotherapy for the major secondary endpoint. The testing will be done simultaneously at the 1-sided 0.1 level of significance for each comparison.

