5.2. Analysis Specifications

5.2.1. Level of Significance

A 2-sided significance level of 0.2 (equivalent to the 1-sided 0.1 level specified in the protocol) will be used for all hypothesis testing and no adjustments for multiple comparisons will be made. Nominal p-values will be presented.

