5.3.3. Analysis Methods for the Primary Estimand (Estimand 1)

5.3.3.1. Main Estimator (Analysis) for the Primary Estimand

The primary endpoint, defined in Section 5.3.1, will be analyzed based on the Primary Estimand (Section 5.3.2). After accounting for the ICEs for the primary estimand (Estimand 1), participants who are missing any or all of the Mayo subscores that comprise the primary endpoint at Week 12 will be considered not to be in clinical response at Week 12 (i.e. nonresponder imputation).

In the primary analysis, data from all participants in the FAS (Section 2.2.2) will be analyzed according to the randomized study intervention regardless of the study intervention they actually received. The treatment difference between combination therapy versus each monotherapy will be tested using a 2-sided CMH chi-square test stratified by corticosteroid use at baseline (yes, no) at the 0.2 significance level. The magnitude of the treatment difference will be estimated by the difference in the proportion of participants achieving clinical response at Week 12 between the combination therapy group and each monotherapy group with a 2-sided 80% confidence interval (CI) calculated based on Wald statistic.

The study will be considered positive if the combination therapy group is significantly different from both monotherapy groups at the 2-sided significance level of 0.2 for the primary endpoint.

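### The SAP tests clinical remission whatever the primary result, while the protocol tests it only if both primary comparisons succeed; the change is not explained

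*SAP*

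**What the plan says.** Protocol 9.4.1.3 makes the remission tests conditional: "If both tests of the primary endpoint are positive, a CMH chi-square test (1-sided) stratified by concomitant use of corticosteroids at baseline" will be used to compare combination with each monotherapy. The synopsis repeats the condition. Once it is met, both remission comparisons are tested without adjustment: "The testing will be done simultaneously at the 1-sided 0.1 level of significance for each comparison".

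SAP 5.4.3.1 says the opposite about the condition: "The testing of the major secondary endpoints will occur at a 2-sided significance level of 0.2 regardless of the significance of the primary endpoint". It adds that there is no multiplicity adjustment and that p-values are nominal. SAP 5.2.1 is consistent with this: a 2-sided level of 0.2 "will be used for all hypothesis testing and no adjustments for multiple comparisons will be made".

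Study success is defined on the primary endpoint alone. Under SAP 5.3.3.1 the study is "considered positive if the combination therapy group is significantly different from both monotherapy groups at the 2-sided significance level of 0.2". Protocol 9 also provides that "Nominal p-values will be displayed for all treatment comparisons", so under either rule the remission p-values appear in the report.

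**The concern.** If the primary endpoint misses against one or both monotherapies, the protocol gives remission no formal test and the SAP gives it two. A remission result called significant after a failed primary would be allowed by one document and ruled out by the other.

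The protocol also places the major secondary endpoint above the other efficacy endpoints, which 9.4.1.4 leaves unadjusted and nominal. SAP 5.4.3.1 and 5.5.3 treat the two classes alike, so that ranking disappears. SAP 5.2.1 takes care to explain that 2-sided 0.2 matches the protocol's 1-sided 0.1, but nothing in the SAP text available explains why the gate went. The SAP's front matter was not available, so an explanation there cannot be excluded.

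**Working it through.** **Inputs from the documents.** 70 per arm, 1:1:1; 1-sided 0.1 per comparison (critical value 1.2816); planned response 75% combination, 55% guselkumab, 55% golimumab (Protocol 9.2). Rates below are in that order.

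**Assumed input.** Remission is 10–20% in every arm. The documents plan no Week 12 remission rate; Protocol 2.1 cites short-term remission below 20% for biologic monotherapy.

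**Method.** At least 1 million simulated trials per scenario: binomial arms of 70, a shared combination arm, and pooled two-proportion z-tests without continuity correction. The gate opens if combination beats both monotherapies on response. Wins are counted for combination only. Remission is drawn as a subset of responders: with baseline Mayo of at least 6, a score of 2 or less is a fall of at least 4 points and at least 4/6 = 67%, and no subscore above 1 means rectal bleeding of 0 or 1, so every remitter is a responder.

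**Reproducing the plan.** Protocol 9.2 claims "approximately 80% power (based on simulations) to achieve both comparisons to monotherapy for the primary endpoint". The simulated gate opens in 81% of trials at 75/55/55% and 69% at 75/60/55%, matching Table 4 (81% and 69%). Across Table 4 the stated power runs from 66% to 90%, so the primary fails in 100 − 90 = 10% to 100 − 66 = 34% of trials.

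**Rough check on the null.** Two comparisons sharing one arm have correlation 0.5. Both exceed 1.2816 in about 3.2% of null trials, so at least one does in 10 + 10 − 3.2 = 16.8%. The first figure is how often the gate opens under the global null, and so caps any gated error there. The second is the approximate ungated error.

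**Results.**

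| Scenario (response rates) | False remission win | No gate (SAP) | Gate (protocol) |
|---|---|---|---|
| Global null, 55/55/55% | at least one | 17–18% | 1.2–1.5% |
| Global null, 55/55/55% | both | 3.0–3.3% | 0.3–0.5% |
| Combination equals guselkumab, 75/75/55% | over guselkumab | 10.0–10.7% | 1.8–2.2% |
| Response as planned, 75/55/55% | at least one | 17–18% | 15.4–15.9% |

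In the last row the gate opens in about 81% of trials, so it removes little.

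**Sensitivity.**
- Over response of 35–75% and remission of 10–40%, the global-null figures span about 16.4–18.1% ungated and 1.0–2.7% gated.
- A CMH test stratified by corticosteroid use (assumed prevalence 30% or 50%, remission 15%) gives 17.5% against 1.3% under the global null, and 10.4% against 1.9–2.0% for guselkumab alone.
- SAP 5.3.3.1 words success as a difference in either direction. With a non-directional gate, the gated figures become 1.4–1.6% (global null) and 2.2–2.4% (over guselkumab).

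**The case against.** The case for leaving this alone is reasonable. This is a Phase 2a proof-of-concept trial whose success rests on the primary. The SAP labels the remission p-values nominal and disclaims adjustment openly. Protocol 9 leaves specific details to the SAP, and the SAP is the later text, since it reports as done an interim analysis that the protocol only plans. No estimate, confidence interval or displayed p-value changes under either rule. Restoring the gate also costs chances of a formal remission claim.

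Most of that stands and limits the weight of the point. Two parts do not. Leaving details to the SAP does not clearly cover reversing a rule the protocol states twice; where 9.4.1.3 does hand something over (alternative remission definitions), it says so. And the nominal label sits beside an instruction to test at a significance level, which invites a claim the protocol would not allow after a failed primary.

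A reader might infer more than the documents support:
- *That the protocol's scheme controls error across the two remission comparisons.* It does not. Once open, the gate leads to two unadjusted tests.
- *That the gate is the only way the two remission analyses differ.* It is the only difference in multiplicity handling. Sidedness, the handling of missing Mayo subscores (Protocol 8.1.1 carries forward; the SAP imputes non-remission) and the COVID-19 intercurrent-event rule also differ, and are separate points.
- *That the unblinded interim look in April 2020 prompted the change.* The SAP describes that look in the past tense, which makes a stated reason more valuable, but nothing in the documents says when or why the rule changed.

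**Conclusion.** The contradiction is real and should be fixed. It concerns what may be claimed for remission after a failed primary; it does not inflate the error of the trial's success criterion, and a reader who infers that would be wrong.

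The contrast of 17–18% with 1.2–1.5% belongs to the global null and should not be quoted as the general effect. The gate also matters when combination adds nothing over one monotherapy. It gives little protection when response behaves as planned and remission alone is null. All figures rest on the assumed remission rates and count wins for combination only. The large gap under the global null holds across the range tried.

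**What to change.** In SAP 5.4.3.1, replace the clause that makes remission testing independent of the primary result with: *only if both primary comparisons are significant in favour of combination therapy (Section 5.3.3.1); otherwise remission estimates, 80% CIs and nominal p-values are reported descriptively, without a claim of significance.* In SAP 5.2.1, add a cross-reference to 5.4.3.1 for the major secondary endpoint.

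This is a change of wording only; data, sample size and outputs stay the same. The price is that formal remission claims are lost when the primary fails. P(at least one remission win), with remission rates assumed:

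| Remission | No gate | Gate, response 75/55/55% | Gate, response 75/60/55% |
|---|---|---|---|
| 30/15/15% | 92% | 76% | 65% |
| 25/15/15% | 75% | 63% | 55% |

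The protocol never granted those claims.

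If the sponsor prefers no gate, amend Protocol 9.4.1.3 and the synopsis to match the SAP, state the change and its reason in the SAP, and label remission results nominal throughout, whatever the primary result. Labelling them descriptive only after a failed primary would bring the gate back under another name.

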5.4.3.2. Subgroup Analyses

Subgroup analyses will be performed (if the number of participants within each subgroup level permits) based on demographic and baseline disease characteristics, baseline concomitant UC medication use, and history of UC-related medications specified in Section 2.3. Note that, for subgroup analyses, the analysis sets are the individual subgroups of the FAS. A forest plot will be produced for all subgroups. Odds ratio of the combination therapy group versus each monotherapy group and the associated 80% CI from a logistic regression model will be provided for each of subgroups. The logistic regression model will include treatment group and corticosteroid use at baseline (yes, no) as the factors. For subgroup analyses of corticosteroid use at baseline (yes, no), treatment group will be the only the factor in the model. The main estimand (Estimand 4) will be used for these subgroup analyses.

5.4.4. Supplementary Estimands

Two supplementary estimands (Estimands 5 and 6) are considered to support the main estimand for the major secondary endpoint (Estimand 4).

5.4.4.1. Estimand 5

In this supplementary estimand for the major secondary endpoint (Estimand 5), all ICEs (Section 5.3.2) will be addressed by the **composite strategy**.

The attributes and strategies for the ICEs that were used for Estimand 2 for the primary endpoint (Section 5.3.4.1) will also be used for this supplementary estimand for the major secondary endpoint (Estimand 5).

5.4.4.2. Estimand 6

In this supplementary estimand for the major secondary endpoint (Estimand 6), all ICEs (Section 5.3.2) will be addressed by the **hypothetical strategy**.

The attributes and strategies for the ICEs that were used for Estimand 3 for the primary endpoint (Section 5.3.4.2) will also be used for this supplementary estimand for the major secondary endpoint (Estimand 6).

5.4.5. Estimators (Analyses) for the Supplementary Estimands

5.4.5.1. Estimator (Analysis) for Estimand 5

For the supplementary analysis of the major secondary endpoint based on Estimand 5, after accounting for the ICEs for this supplementary estimand, participants who have a missing clinical remission status at Week 12 will be considered not to be in clinical remission at Week 12 (i.e. nonresponder imputation).

In this supplementary analysis for the major secondary endpoint, data from all participants in the FAS (Section 2.2.2) will be analyzed according to the randomized study intervention regardless of the study intervention they actually received. The analysis method is same as that for the main estimator (analysis) for the primary estimand (Estimand 1). Refer to Section 5.3.3.1 for details.

5.4.5.2. Estimator (Analysis) for Estimand 6

For the supplementary analysis of the major secondary endpoint based on Estimand 6, after accounting for the ICEs for this supplementary estimand, the missing status of clinical remission at Week 12 will be imputed using MI. For participants with missing status of clinical remission at Week 12, their clinical remission status at Week 12 will be derived from the imputed Mayo subscores in MIMayoData1 that has been created in Section 5.3.5.2.

The analysis method based on this supplementary estimand (Estimand 6) for the major secondary endpoint is same as the analysis method based on the supplementary estimand (Estimand 3) for the primary endpoint. Refer to Section 5.3.5.2 for details.

5.5. Other Efficacy Endpoints

In addition to the primary and major secondary endpoints, other efficacy endpoints related to disease status, HRQoL outcomes (including fatigue), and inflammatory biomarkers will also be analyzed. This section outlines the definitions (Section 5.5.1) and analyses (Section 5.5.2) of the other efficacy endpoints.

Clinical Endpoints

- Clinical response at Week 38

-
- Clinical response at Week 38 by clinical response status at Week 12
 - Clinical remission at Week 38
 - Clinical remission at Week 38 by clinical remission status at Week 12
 - Clinical remission at Week 38 by clinical response status at Week 12
 - Change from baseline in Mayo score at Weeks 12 and 38.
 - Change from baseline in partial Mayo score by visit through Week 38.
 - Change from baseline in modified Mayo score at Weeks 12 and 38.
 - Change from baseline in Mayo subscores by visit through Week 38.
 - Modified Mayo response at Weeks 12 and 38
 - Modified Mayo response at Week 38 by modified Mayo response status at Week 12
 - Symptomatic remission by visit through Week 38
 - Endoscopic healing at Weeks 12 and 38
 - Endoscopic healing at Week 38 by endoscopic healing status at Week 12
 - Endoscopic normalization at Weeks 12 and 38.
 - Endoscopic normalization at Weeks 38 by endoscopic normalization status at Week 12
 - Clinical response, clinical remission, and endoscopic healing at Weeks 12 and 38 by negative response signature status at baseline.
 - Clinical remission by alternative definitions:
 - Clinical remission (UNIFI definition) at Weeks 12 and 38
 - Clinical remission (UNIFI definition) at Week 38 by clinical remission (UNIFI definition) status at Week 12
 - Clinical remission (Health Authority definition 1) at Weeks 12 and 38
 - Clinical remission (Health Authority definition 1) at Week 38 by clinical remission (Health Authority definition 1) status at Week 12
 - Clinical remission (Health Authority definition 2) by visit at Weeks 12 and 38
 - Clinical remission (Health Authority definition 2) at Week 38 by clinical remission (Health Authority definition 2) status at Week 12
 - Histologic healing at Weeks 12 and 38
 - Mucosal healing at Weeks 12 and 38
 - Histologic remission at Weeks 12 and 38
 - Histologic-endoscopic mucosal healing at Weeks 12 and 38
 - Deep histologic-endoscopic mucosal healing at Weeks 12 and 38
 - Geboes total score, high activity subscore, and low activity subscore at Weeks 0, 12, and 38
 - Roberts Histologic Index (RHI)-based histologic remission at Weeks 12 and 38

-
- Nancy Histologic Index (NHI)-based histologic remission at Weeks 12 and 38
 - Ulcerative Colitis Endoscopic Index of Severity (UCEIS) score at Weeks 0, 12, and 38 by the level of Mayo endoscopy score at the corresponding visit
 - Change from baseline in UCEIS score at Weeks 12 and 38
 - UCEIS score ≤ 4 at Weeks 12 and 38
 - Clinical remission and not receiving concomitant corticosteroids at Week 12
 - Clinical response and not receiving concomitant corticosteroids at Week 12
 - Clinical remission and not receiving concomitant corticosteroids at Week 38
 - Clinical response and not receiving concomitant corticosteroids at Week 38
 - Clinical remission and not receiving concomitant corticosteroids at Week 38 by status of clinical remission and not receiving concomitant corticosteroids at Week 12
 - Clinical response and not receiving concomitant corticosteroids at Week 38 by status of clinical response and not receiving concomitant corticosteroids at Week 12
 - ICEs (listed in Section 5.3.2) prior to Week 12 and prior to Week 38
 - Mayo score missing at Week 12 by reason causing missing (including COVID-19 related) and at Week 38 by reason causing missing (including COVID-19 related)
 - Endoscopy subscore missing at Week 12 by reason causing missing (including COVID-19 related) and at Week 38 by reason causing missing (including COVID-19 related)

Inflammatory Biomarkers (CRP and Fecal Calprotectin)

- Change from baseline in CRP by visit through Week 38
- Change from baseline in CRP by visit through Week 38 among participants with abnormal CRP concentration at baseline
- Change from baseline in fecal calprotectin concentration by visit through Week 38
- Change from baseline in fecal calprotectin concentration by visit through Week 38 among participants with abnormal fecal calprotectin concentration at baseline
- Normalization of CRP concentration by visit through Week 38 among participants with abnormal CRP concentration at baseline
- Normalization of fecal calprotectin concentration by visit through Week 38 among participants with abnormal fecal calprotectin concentration at baseline

HRQoL Endpoints

- Change from baseline in the total score of the Inflammatory Bowel Disease Questionnaire (IBDQ) by visit through Week 38
- A >20-point improvement from baseline in the IBDQ score by visit through Week 38
- Change from baseline in the 7 domain scores (norm-based) and the abdominal pain intensity score of Patient-Reported Outcomes Measurement Information System (PROMIS)-29 by visit through Week 38

- A ≥ 5 -point improvement from baseline in PROMIS-29 domain scores (norm-based) and pain intensity score by visit through Week 38
- Change from baseline in the PROMIS Fatigue Short Form 7a total score by visit through Week 38
- Fatigue response (≥ 5 -point improvement) based on the PROMIS Fatigue Short Form 7a by visit through Week 38

